7.4 Schedule of Treatment Visits

Avelumab will be administered every two weeks starting at Week 1. Dosing may be delayed in response to certain toxicities, as described under Section 10.

Trabectedin will be given every three weeks for Cycle 1 (Week 1) and Cycle 2 (Week 4), and then will be given every 4 weeks (Week 7, Week 11,...). For toxicity management after Cycle 2 (Week 4) Day 1, trabectedin administration may delay to Q5W, as clinically indicated for toxicity management. Delays of trabectedin beyond 5 weeks may be allowed but require written approval from the Sponsor-Investigator.

Administration of either study drug may vary ± 3 days from planned date.

The administration of study drugs during the first 12 weeks (first response assessment timepoint), assuming no dose delays or modifications due to toxicity, is shown below.

The study calendar will be managed in Weeks, with each dose of each drug being noted by a Cycle. For example, assuming there are no deviations from the planned schedule events, Week 1 will have Cycle 1 of avelumab and trabectedin. Week 3 will have Cycle 2 of avelumab, Week 4 will have Cycle 2 of trabectedin, Week 5 will have Cycle 3 of avelumab, Week 7 will have Cycle 4 of avelumab and Cycle 3 of trabectedin, etc. This may change based on dose delays or modifications. Weeks should be counted sequentially regardless of what number the dose of each agent is.

	Week											
Drug	1	2	3	4	5	6	7	8	9	10	11	12*
Avelumab	•		•		•		•		•		•	
Trabectedin	•			•			•				•	

*Response assessment.

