10.0 MANAGEMENT OF TOXICITY AND COMPLICATIONS

10.1 Adverse Drug Reactions (ADRs) Related to Avelumab

Adverse Drug Reactions Requiring Avelumab Discontinuation or Modifications

The following ADR/AEs require permanent treatment discontinuation of avelumab if they are not expected toxicities of trabectedin and their management is not specifically outlined below:

Any Grade 4 ADR/AEs require treatment discontinuation with avelumab except for single laboratory values out of normal range that are unlikely related to study treatment as assessed by the Investigator, do not have any clinical correlate, and resolve or return to baseline within 7 days with adequate medical management

Any Grade 3 ADR/AEs require treatment discontinuation with avelumab except for any of the following:

- Transient (≤ 6 hours) Grade 3 flu-like symptoms or fever, which is controlled with medical management
- Transient (≤ 24 hours) Grade 3 fatigue, local reactions, headache, nausea, emesis that resolves to Grade ≤ 1
- Laboratory values out of normal range that may be related to trabectedin.
- Tumor flare phenomenon defined as local pain, irritation, or rash localized at sites of known or suspected tumor
- Change in ECOG PS to ≥ 3 that does not resolve to ≤ 2 within 14 days (infusions should not be given on the following cycle, if the ECOG PS is ≥ 3 on the day of study drug administration). Subjects may continue on study with ECOG PS ≤ 2 .

Any Grade 2 ADR/AE should be managed as follows:

- If a Grade 2 ADR/AE resolves to Grade ≤ 1 by the last day of the current week, treatment may continue.
- If a Grade 2 ADR/AE does not resolve to Grade ≤ 1 by the last day of the current week, infusions should not be given on the following week. If at the end of the following week the event has not resolved to Grade 1, the subject should permanently discontinue treatment with avelumab ADR/AE (except for hormone insufficiencies, that can be managed by replacement therapy; for these hormone insufficiencies, up to 2 subsequent doses may be omitted).

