10.3 Toxicity of Trabectedin

Trabectedin is given as standard of care and does have notable toxicities. The following are to be considered expected toxicities of trabectedin:

- Leukopenia (with neutropenia as the predominant component)
- Malaise
- Infection/sepsis
- Transaminase Elevation
- CK elevation
- Bilirubin or Alkaline phosphatase elevation
- Fatigue
- Nausea/vomiting
- Renal toxicity

Rhabdomyolysis is an unusual but well-described toxicity of trabectedin. If rhabdomyolysis is observed in a single case, this should not be considered a DLT but if multiple cases are seen, this must be reviewed by the DSMB.

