10.4 Dose Modification of Trabectedin

Trabectedin is to be started at 1.5 mg/m². After the first week, the dose may be reduced if clinically indicated for toxicity management. Dose reductions will be noted in the subject's clinical record or research shadow chart.

As per standard practice, the subjects first dose reduction will be to 1.2 mg/m² and the second dose reduction will be to 1 mg/m². Dose reductions beyond 1 mg/m² are not permitted. If a subject is unable to tolerate a dose of 1mg/m², they must come off study. Trabectedin may be spaced out initially to 4 weeks and then to 5 weeks, as needed for toxicity management. If, in the opinion of the treating investigator, trabectedin needs to be spaced out greater than 5 weeks, Sponsor-Investigator approval is required.

Trabectedin dose reduction is required for the following adverse reactions:

- ANC < 1000/μL with fever and infection
- ANC <500/μL lasting > 5 days
- Platelets < 25,000/ μL
- Grade 3 or higher nausea and vomiting that persists despite a full anti-emetic regimen
- Grade 3 transaminitis not recovering to <2.5 x ULN or subject's baseline by 3 weeks post infusion
- Grade 3 Alk Phos Elevation not recovering to <2.5 x ULN or subject's baseline by 3 weeks post-infusion
- Total Bilirubin > 2.5 x ULN (direct bilirubin can be used if there is suspicion for Gilbert's syndrome)
- CK > 2.5 x ULN
- EF <45%

Subjects receiving the 1mg/m² dose of trabectedin with liver involvement from their cancer or baseline liver dysfunction, who are otherwise tolerating treatment well and appear to be benefiting from treatment on the study, may continue at the 1mg/m² after recovery from their liver dysfunction to grade 2, with Sponsor-Investigator approval.

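### Section 10.1 is harsher at Grade 2 than at Grade 3 for trabectedin-related laboratory values that 10.3 omits, platelets being the clear case

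*Combined protocol and SAP*

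**What the plan says.** All references are to the combined protocol and SAP.

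- **10.1, lead-in.** Adverse events require permanent avelumab discontinuation "if they are not expected toxicities of trabectedin and their management is not specifically outlined below". No grade limit is attached to this condition.
- **10.1, Grade 3.** The exceptions to stopping avelumab include: "Laboratory values out of normal range that may be related to trabectedin".
- **10.1, Grade 2.** An event not back to Grade 1 or better by the last day of the current week means no infusion in the following week. Then: "If at the end of the following week the event has not resolved to Grade 1, the subject should permanently discontinue treatment with avelumab". The one exception is for hormone insufficiencies manageable by replacement; "for these hormone insufficiencies, up to 2 subsequent doses may be omitted".
- **10.3.** "The following are to be considered expected toxicities of trabectedin": leukopenia (mainly neutropenia), malaise, infection or sepsis, transaminase elevation, CK elevation, bilirubin or alkaline phosphatase elevation, fatigue, nausea or vomiting, and renal toxicity. Thrombocytopenia is not on the list.
- **10.4.** The only platelet entry is "Platelets < 25,000" per µL, as a reason for trabectedin dose reduction. More generally, "Trabectedin may be spaced out initially to 4 weeks and then to 5 weeks, as needed for toxicity management".
- **9.1.** An abnormal laboratory value is recorded as an adverse event only if it needs intervention, results in a serious event, or leads to study termination or to interruption or discontinuation of treatment.

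**The concern.** Section 10.1 accepts that an abnormal laboratory value possibly caused by the partner drug should not cost the subject avelumab, but it writes that principle only into the Grade 3 list. For a value that the lead-in does not protect, the milder grade therefore carries the heavier consequence.

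A subject could lose the experimental drug permanently for a laboratory effect of trabectedin, at a grade where 10.4 requires no trabectedin reduction and allows trabectedin to be spaced and resumed. The investigator would have to follow an inverted rule or depart from the text case by case. The event is foreseeable: section 2.6 reports severe thrombocytopenia in 10% of trabectedin cycles at the recommended dose. That figure is not a Grade 2 rate, but it shows that platelets are a known target of the drug.

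**Working it through.** The plan gives no figure to reproduce. The check compares texts and then counts days.

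**1. Which Grade 2 laboratory values does the lead-in protect?** It excludes expected trabectedin toxicities, and 10.3 uses the same phrase for its list.

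| Laboratory value, trabectedin-related | On the 10.3 list? | Grade 2, persistent | Grade 3 |
|---|---|---|---|
| Neutrophils, AST/ALT, CK, bilirubin, alkaline phosphatase, renal | Yes | Permanent stop does not apply (lead-in) | Does not end avelumab under 10.1 |
| Platelets | No | Permanent stop applies as written | Does not end avelumab (Grade 3 laboratory exception) |

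**2. Is a Grade 2 platelet count managed elsewhere in Section 10?** The 10.4 entry is below 25,000/µL, which 4.1.2 labels Grade 4. No table in 10.2 names platelets, and Table 2 in 10.2.2.4 is for toxicities probably related to avelumab. The second limb of the lead-in therefore does not protect the count either.

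**3. Does the count qualify as an adverse event?** Only through 9.1. The plausible route is that the investigator delays trabectedin because of it, and the delay is treated as an interruption.

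**4. How quickly does the stop come?** Let onset fall on day d of the current week (d = 1 to 7), with the onset day counted as day 1. The end of the following week is then day 15 − d.
- d = 1: 15 − 1 = 14.
- d = 7: 15 − 7 = 8.

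The stop falls on day 8 to 14. Avelumab is planned in odd weeks. With onset in an odd week, no planned dose falls in the following week, so 0 doses are omitted before the stop; with onset in an even week, 1 is.

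**5. Illustration on the planned calendar.** A Grade 2 count on day 1 of week 7 leads to a delay of trabectedin Cycle 3. Section 7.4 states: "For toxicity management after Cycle 2 (Week 4) Day 1, trabectedin administration may delay to Q5W". Week 4 + 5 weeks = week 9, with no special approval needed. Avelumab is planned in weeks 1, 3, 5, 7, 9 and 11, which is 6 doses before the week-12 scan. If the week-7 dose is given (the hold starts only in the following week) and the count is still Grade 2 at the end of week 8, avelumab ends after weeks 1, 3, 5 and 7: 4 of 6 doses, with 2 lost. At Grade 3, 10.1 would not end it.

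This illustration needs an unscheduled blood count. Appendix C requires no evaluation after week 7 in weeks without treatment, and week 8 has none here, so the next required count is at the week-9 visit.

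**The case against.** The strongest reply is that the protocol, read as a whole, never meant this.

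- **10.3 need not be closed.** 4.1.2 refers to Section 10 as a whole for expected toxicities, and 10.4 lists low platelets among trabectedin adverse reactions. 9.3 ties *unexpected* to what has not been seen in earlier studies, and 9.8.3 uses the trabectedin package insert. However, 10.3 repeats the lead-in's own phrase over a definite list. The 10.4 entry reaches only counts below 25,000/µL. 9.3 defines unexpected events in general, and 9.8.3 is limited to regulatory reporting.
- **Trabectedin toxicity is sent elsewhere.** The note to Table 2 directs it to the protocol or, where treatment is not specified, standard of care, and 10.4 allows spacing for any toxicity. The note leads back to the protocol, which includes 10.1. The lead-in asks for *specific* management; if general permission to space trabectedin were enough, the 10.3 list and the Grade 3 laboratory exception would have little purpose.
- **The heading of 10.1 concerns avelumab reactions.** The lead-in and the Grade 3 exception both deal with trabectedin effects, so the heading cannot exclude them.
- **Investigator discretion under 9.0.** It covers events the protocol does not go on to describe, and 10.1 describes any Grade 2 event.

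Three parts of the reply stand. The trigger is narrow, because 10.4 requires no action for a Grade 2 count and 9.1 keeps most such counts from being adverse events. The rule says *should*. And removing the inversion does not require waiving the one-week hold.

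A reader might also infer more than the text supports:

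- **That every Grade 2 trabectedin laboratory effect ends avelumab.** The lead-in and 10.3 already exempt most of them.
- **That avelumab's own effects are treated several times more leniently.** The comparison would be with the 12-week persistence limit under Other irAEs (12 × 7 = 84 days; 84 / 14 = 6). Avelumab is withheld during that time, so it is not continued treatment.

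**Conclusion.** Wrong as written, and minor. For a Grade 2 laboratory value that is neither on the 10.3 list nor managed elsewhere in Section 10, the text calls for a permanent avelumab stop on day 8 to 14, while the same value at Grade 3 does not end avelumab if it may be due to trabectedin. Platelets are the clear case.

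This rests on three conditions: 10.3 is the list that the lead-in means; the count qualifies as an adverse event under 9.1; and the investigator follows the *should*. A reader might infer a loss of power or damage to the response endpoint, but the documents give no Grade 2 platelet frequency and no basis for deriving one. The 4-of-6-dose illustration shows what one subject could lose if a count is taken at the end of week 8; it is not an expected loss. The handling of Grade 4 is not part of this point.

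**What to change.** In the Grade 2 paragraph of 10.1, extend the hormone-insufficiency exception to the permanent stop so that it also covers the category already exempt at Grade 3 ("Laboratory values out of normal range that may be related to trabectedin"), unless a table in 10.2 gives a rule for that value. The one-week hold may stay.

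Leave the Grade 4 rule, 10.3 and the DLT definitions as they are. Adding thrombocytopenia to 10.3 instead would be narrower, but it could have side effects: 16.2 defines DLTs as unexpected toxicities, and the Phase 2 hold in 4.1.2 counts unexpected events, so a longer list of expected toxicities might remove platelet events from both.

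The cost is one clause, with no change to procedures or sample size. The downside is slightly more avelumab exposure after Grade 2 laboratory abnormalities whose cause is uncertain.

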10.2 Avelumab-Specific Adverse Events or Adverse Drug Reactions

10.2.1 Symptoms of Infusion-Related Reactions

Symptoms of infusion-related reactions include:

- Fever
- Chills
- Rigors
- Dyspnoea, wheezing
- Diaphoresis
- Headache

10.2.2 Management of Infusion-Related Reactions

10.2.2.1 Table 1: Treatment Modification for Symptoms of Infusion-Related Reactions

NCI-CTCAE Grade	Treatment Modification for Study Drug
Grade 1 – mild Mild transient reaction; infusion interruption not indicated; intervention not indicated.	Decrease the avelumab infusion rate by 50% and monitor closely for any worsening. The total infusion time for study drug should not exceed 120 minutes.
Grade 2 – moderate Therapy or infusion interruption indicated but responds promptly to symptomatic treatment (for example, antihistamines, NSAIDs, narcotics, IV fluids); prophylactic medications indicated for ≤ 24 h.	Temporarily discontinue avelumab infusion. Resume infusion at 50% of previous rate once infusion-related reaction has resolved or decreased to at least Grade 1 in severity, and monitor closely for any worsening.
Grade 3 or Grade 4 – severe or life-threatening Grade 3: Prolonged (for example, not rapidly responsive to symptomatic medication and/or brief interruption of infusion); recurrence of symptoms following initial improvement; hospitalization indicated for clinical sequelae. Grade 4: Life-threatening consequences; urgent intervention indicated.	Stop the avelumab infusion immediately and disconnect infusion tubing from the subject. Subjects have to be withdrawn immediately from avelumab treatment and must not receive any further avelumab treatment.

If avelumab infusion rate has been decreased by 50% or interrupted due to an infusion reaction, it must remain decreased for the next scheduled infusion. If no infusion reaction is observed in the next scheduled infusion, the infusion rate may be returned to baseline at the subsequent infusions based on treating investigator's medical judgment. If hypersensitivity reaction occurs, the subject must be treated according to the best available medical practice.

10.2.2.2 Severe Hypersensitivity Reactions and Flu-Like Symptoms

If hypersensitivity reaction occurs, the subject must be treated according to the best available medical practice. Subjects should be instructed to report any delayed reactions to the Investigator immediately.

For prophylaxis of flu-like symptoms, 25 mg of indomethacin or comparable nonsteroidal anti-inflammatory drug (NSAID) dose (for example, ibuprofen 600 mg, naproxen sodium 500 mg) may be administered 2 hours before and 8 hours after the start of each dose of avelumab IV infusion, as indicated per standard institutional practice. Alternative treatments for fever (for example, acetaminophen) may be given to subjects at the discretion of the Investigator.

10.2.2.3 Tumor Lysis Syndrome

In addition, avelumab can induce antibody-dependent cell-mediated cytotoxicity and can therefore theoretically cause tumor lysis syndrome. Should this occur, subjects should be treated per standard of care and the management algorithm listed in the appendix ([Howard 2011](#)). Because tumor lysis is almost never seen in soft tissue sarcoma subjects with the exception of several case reports, all subjects should be treated as having a low risk for tumor lysis syndrome.

10.2.2.4 Immune-Related Adverse Events

Since inhibition of PD-L1 stimulates the immune system, immune-related AEs (irAEs) may occur. Treatment of irAEs is mainly dependent upon severity (NCI-CTCAE grade):

Grade 1 to 2: treat symptomatically or with moderate dose steroids, more frequent monitoring

Grade 1 to 2 (persistent): manage similar to high grade AE (Grade 3 to 4)

Grade 3 to 4: treat with high dose corticosteroids

Table 2 Management of Immune-mediated Adverse Reactions: Guidance in this table is relevant to toxicities probably related to Avelumab. For toxicity attributed to trabectedin, treat according to the protocol or standard of care if treatment is not otherwise specified.

Gastrointestinal irAEs		
Severity of Diarrhea / Colitis (NCI-CTCAE v4)	Management	Follow-up
Grade 1 Diarrhea: < 4 stools/day over Baseline Colitis: asymptomatic	Continue avelumab therapy Symptomatic treatment (e.g. loperamide)	Close monitoring for worsening symptoms Educate subject to report worsening immediately If worsens: Treat as Grade 2, 3 or 4.
Grade 2 Diarrhea: 4 to 6 stools per day over Baseline; IV fluids indicated < 24 hours; not interfering with ADL Colitis: abdominal pain; blood in stool	Withhold avelumab therapy Symptomatic treatment	If improves to Grade ≤ 1: Resume avelumab therapy If persists > 5-7 days or recurs: Treat as Grade 3 or 4.
Grade 3 to 4 Diarrhea (Grade 3): ≥ 7 stools per day over Baseline; incontinence; IV fluids ≥ 24 h; interfering with ADL Colitis (Grade 3): severe abdominal pain, medical intervention indicated, peritoneal signs Grade 4: life-threatening, perforation	Withhold avelumab for Grade 3. Permanently discontinue avelumab for Grade 4 or recurrent Grade 3. 1.0 to 2.0 mg/kg/day prednisone IV or equivalent Add prophylactic antibiotics for opportunistic infections. Consider lower endoscopy.	If improves: Continue steroids until Grade ≤ 1, then taper over at least 1 month; resume avelumab therapy following steroids taper (for initial Grade 3). If worsens, persists > 3 to 5 days, or recurs after improvement: Add infliximab 5mg/kg (if no contraindication). Note: infliximab should not be used in cases of perforation or sepsis.

Dermatological irAEs		
Grade of Rash (NCI-CTCAE v4)	Management	Follow-up
Grade 1 to 2 Covering \leq 30% body surface area	Continue avelumab therapy Symptomatic therapy (for example, antihistamines, topical steroids)	If persists > 1 to 2 weeks or recurs: Withhold avelumab therapy. Consider skin biopsy. Consider 0.5-1.0 mg/kg/day prednisone or equivalent. Once improving, taper steroids over at least 1 month, consider prophylactic antibiotics for opportunistic infections, and resume avelumab therapy following steroids taper. If worsens: Treat as Grade 3 to 4.
Grade 3 to 4 Grade 3: Covering > 30% body surface area; Grade 4: Life threatening consequences	Withhold avelumab for Grade 3. Permanently discontinue for Grade 4 or recurrent Grade 3. Consider skin biopsy, Dermatology consult, 1.0 to 2.0 mg/kg/day prednisone or equivalent. Add prophylactic antibiotics for opportunistic infections.	If improves to Grade \leq 1: Taper steroids over at least 1 month; resume avelumab therapy following steroids taper (for initial Grade 3).

Pulmonary irAEs		
Grade of Pneumonitis (NCI-CTCAE v4)	Management	Follow-up
Grade 1 Radiographic changes only	Consider withholding avelumab therapy. Monitor for symptoms every 2 to 3 days. Consider Pulmonary and Infectious Disease consults.	Re-assess at least every 3 weeks If worsens: Treat as Grade 2 or Grade 3 to 4.
Grade 2 Mild to moderate new symptoms	Withhold avelumab therapy. Pulmonary and Infectious Disease consults. Monitor symptoms daily; consider hospitalization. 1.0 to 2.0 mg/kg/day prednisone or equivalent. Add prophylactic antibiotics for opportunistic infections. Consider bronchoscopy, lung biopsy .	Re-assess every 1 to 3 days. If improves: When symptoms return to Grade \leq 1, taper steroids over at least 1 month, and then resume avelumab therapy following steroids taper. If not improving after 2 weeks or worsening or for recurrent Grade 2: Treat as Grade 3 to 4.
Grade 3 to 4 Grade 3: Severe new symptoms; New/worsening hypoxia; Grade 4: Life-threatening	Permanently discontinue avelumab therapy. Hospitalize. Pulmonary and Infectious Disease consults. 1.0 to 2.0 mg/kg/day prednisone or equivalent. Add prophylactic antibiotics for opportunistic infections. Consider bronchoscopy, lung biopsy.	If improves to Grade \leq 1: Taper steroids over at least 1 month If not improving after 48 hours or worsening: Add additional immunosuppression (for example, infliximab, cyclophosphamide, IV immunoglobulin, or mycophenolate mofetil)

Hepatic irAEs		
Grade of Liver Test Elevation (NCI-CTCAE v4)	Management	Follow-up
Grade 1 Grade 1 AST or ALT > ULN to 3.0 x ULN and/or Total bilirubin > ULN to 1.5 x ULN	Continue avelumab therapy.	Continue liver function monitoring If worsens: Treat as Grade 2 or 3 to 4.
Grade 2 AST or ALT > 3.0 to ≤ 5 x ULN and / or total bilirubin > 1.5 to ≤ 3 x ULN (this is common for trabectedin)	Withhold avelumab therapy. Increase frequency of monitoring to every 3 days.	If returns to Grade ≤ 1 or Baseline: Resume routine monitoring; resume avelumab therapy. If elevation persists > 5 to 7 days or worsens: Treat as Grade 3 to 4.
Grade 3 to 4 AST or ALT > 5 x ULN and / or total bilirubin > 3 x ULN	Permanently discontinue avelumab therapy. Increase frequency of monitoring to every 1 to 2 days. 1.0 to 2.0 mg/kg/day prednisone or equivalent. Add prophylactic antibiotics for opportunistic infections. Consult gastroenterologist/hepatologist. Consider obtaining MRI/CT scan of liver and liver biopsy if clinically warranted.	If returns to Grade ≤ 1 or baseline: Taper steroids over at least 1 month If does not improve in > 3 to 5 days, worsens or rebounds: Add mycophenolate mofetil 1 gram (g) twice daily. If no response within an additional 3 to 5 days, consider other immunosuppressants per local guidelines.

Endocrine irAEs		
Endocrine Disorder	Management	Follow-up
Grade 1 or Grade 2 endocrinopathies (hypothyroidism, hyperthyroidism, adrenal insufficiency, type I diabetes mellitus)	
Continue avelumab therapy. Endocrinology consult if needed.
 
Start thyroid hormone replacement therapy (for hypothyroidism), anti-thyroid treatment (for hyperthyroidism), corticosteroids (for adrenal insufficiency) or insulin (for Type I diabetes mellitus) as appropriate.
 
Rule-out secondary endocrinopathies (i.e. hypopituitarism / hypophysitis)
	
Continue hormone replacement/suppression and monitoring of endocrine function as appropriate.

Grade 3 or Grade 4 endocrinopathies (hypothyroidism, hyperthyroidism, adrenal insufficiency, type I diabetes mellitus)	
Withhold avelumab therapy. Consider hospitalization. Endocrinology consult.
 
Start thyroid hormone replacement therapy (for hypothyroidism), anti-thyroid treatment (for hyperthyroidism), corticosteroids (for adrenal insufficiency) or insulin (for type I diabetes mellitus) as appropriate.
 
Rule-out secondary endocrinopathies (i.e. hypopituitarism / hypophysitis)
	
Resume avelumab once symptoms and/or laboratory tests improve to Grade ≤ 1 (with or without hormone replacement/suppression).
 
Continue hormone replacement/suppression and monitoring of endocrine function as appropriate.

Hypopituitarism/Hypophysitis (secondary endocrinopathies)	
If secondary thyroid and/or adrenal insufficiency is confirmed (i.e. subnormal serum FT4 with inappropriately low TSH and/or low serum cortisol with inappropriately low ACTH) :
 
Refer to endocrinologist for dynamic testing as indicated and measurement of other hormones (FSH, LH, GH/IGF-1, PRL, testosterone in men, estrogens in women). Hormone replacement/suppressive therapy as appropriate. Perform pituitary MRI and visual field examination as indicated.
 
If hypophysitis confirmed:
 
Continue avelumab if mild symptoms with normal MRI. Repeat the MRI in 1 month. Withhold avelumab if moderate, severe or life-threatening symptoms of hypophysitis and/or abnormal MRI. Consider hospitalization. Initiate corticosteroids (1 to 2 mg/kg/day prednisone or equivalent) followed by corticosteroids taper during at least 1 month. Add prophylactic antibiotics for opportunistic infections.
	
Resume avelumab once symptoms and hormone tests improve to Grade ≤ 1 (with or without hormone replacement).
 
In addition, for hypophysitis with abnormal MRI, resume avelumab only once shrinkage of the pituitary gland on MRI/CT scan is documented.
 
Continue hormone replacement/suppression therapy as appropriate.

Renal irAEs		
Grade of Creatinine Increased (NCI-CTCAE v4)	Initial Management	Follow-up Management
Grade 1 Creatinine increased > ULN to 1.5 x ULN	Continue avelumab therapy.	Continue renal function monitoring. If worsens: Treat as Grade 2 to 3 or 4.
Grade 2 to 3 Creatinine increased > 1.5 and ≤ 6 x ULN	Withhold avelumab therapy. Increase frequency of monitoring to every 3 days. 1.0 to 2.0 mg/kg/day prednisone or equivalent. Add prophylactic antibiotics for opportunistic infections. Consider renal biopsy.	If returns to Grade ≤1 or baseline: Taper steroids over at least 1 month, and resume avelumab therapy following steroids taper. If worsens: Treat as Grade 4.
Grade 4 Creatinine increased > 6 x ULN	Permanently discontinue avelumab therapy. Monitor creatinine daily. 1.0 to 2.0 mg/kg/day prednisone or equivalent. Add prophylactic antibiotics for opportunistic infections. Consider renal biopsy. Nephrology consult.	If returns to Grade ≤1 or baseline: Taper steroids over at least 1 month.

Cardiac irAEs		
Myocarditis	Management	Follow-up
New onset of cardiac signs or symptoms and / or new laboratory cardiac biomarker elevations (e.g. troponin, CK-MB, BNP) or cardiac imaging abnormalities suggestive of myocarditis.	Withhold avelumab therapy. Hospitalize. In the presence of life threatening cardiac decompensation, consider transfer to a facility experienced in advanced heart failure and arrhythmia management. Cardiology consult to establish etiology and rule-out immune-mediated myocarditis. Guideline based supportive treatment as per cardiology consult.* Consider myocardial biopsy if recommended per cardiology consult.	If symptoms improve and immune-mediated etiology is ruled out, re-start avelumab therapy. If symptoms do not improve/worsen, viral myocarditis is excluded, and immune-mediated etiology is suspected or confirmed following cardiology consult, manage as immune-mediated myocarditis.
Immune-mediated myocarditis	Permanently discontinue avelumab. Guideline based supportive treatment as appropriate as per cardiology consult.* 1.0 to 2.0 mg/kg/day prednisone or equivalent. Add prophylactic antibiotics for opportunistic infections.	Once improving, taper steroids over at least 1 month. If no improvement or worsening, consider additional immunosuppressants (e.g. azathioprine, cyclosporine A).

*Local guidelines, or eg. ESC or AHA guidelines ESC guidelines website: https://www.escardio.org/Guidelines/Clinical-Practice-Guidelines AHA guidelines website: http://professional.heart.org/professional/GuidelinesStatements/searchresults.jsp?q=&y=&t=1001
		

Other irAEs (not described above)		
Grade of other irAEs (NCI-CTCAE v4)	Initial Management	Follow-up Management
Grade 2 or Grade 3 clinical signs or symptoms suggestive of a potential irAE	Withhold avelumab therapy pending clinical investigation.	If irAE is ruled out , manage as appropriate according to the diagnosis and consider re-starting avelumab therapy If irAE is confirmed , treat as Grade 2 or 3 irAE.
Grade 2 irAE or first occurrence of Grade 3 irAE	Withhold avelumab therapy. 1.0 to 2.0 mg/kg/day prednisone or equivalent. Add prophylactic antibiotics for opportunistic infections. Specialty consult as appropriate.	If improves to Grade ≤ 1 or baseline : Taper steroids over at least 1 month and resume avelumab therapy following steroids taper.
Recurrence of same Grade 3 irAEs	Permanently discontinue avelumab therapy. Up to 2.0 mg/kg/day prednisone or equivalent. Add prophylactic antibiotics for opportunistic infections. Specialty consult as appropriate.	If improves to Grade ≤ 1 or baseline : Taper steroids over at least 1 month.
Grade 4	Permanently discontinue avelumab therapy. Up to 2.0 mg/kg/day prednisone or equivalent and/or other immunosuppressant as needed. Add prophylactic antibiotics for opportunistic infections. Specialty consult.	If improves to Grade ≤ 1 or baseline : Taper steroids over at least 1 month
Requirement for 10 mg per day or greater prednisone or equivalent for more than 12 weeks for reasons other than hormonal replacement for adrenal insufficiency Persistent Grade 2 or 3 irAE lasting 12 weeks or longer	Permanently discontinue avelumab therapy. Specialty consult.	

**Grade 2 hepatic toxicity is common with trabectedin and grade 3 can happen occasionally. While it is necessary to include these treatment guidelines for safety, in reality it is more likely that hepatic toxicity will be related to trabectedin.

